6.3 Sample Size

Up to 250 subjects will be enrolled in the study. The study shall be continued until at least 30 positive and 30 negative tests results are obtained.

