Clinical Protocol BIOZEK

Title: **“Open label, Single-Center Study utilizing BIOZEK COVID-19 Antigen Rapid Test.”**

Comparison of Biozek COVID-19 Antigen Rapid test results performed on self-collected samples by the subjects, to results of COVID-19 RT-PCR as a standard of care.

Short title: Comparison of BIOZEK Antigen Rapid Test to COVID-19 RT-PCR.

Protocol Number: Biozek-ARTC-US/002/4-12-2021

Product: BIOZEK COVID-19 Antigen Rapid Test Cassette Nasopharyngeal Swab

BIOZEK COVID-19 Antigen Rapid Test Cassette Oral Fluid

Principal Investigator: [name]., PhD

Co-Principal Investigator: [name]

Study Coordinator: [name]

Version: Final 4.0

Date: June 1, 2021

CONFIDENTIALITY STATEMENT

The information contained in this document, particularly unpublished data, is the property or under control of Biozek medical and is provided to you in confidence as an investigator, potential investigator, or consultant, for review by you, your staff, and an applicable Institutional Review Board or Independent Ethics Committee. The information is only to be used by you in connection with authorized clinical studies of the investigational drug described in the protocol. You will not disclose any of the information to others without written authorization from Biozek Company, except to the extent necessary to obtain informed consent from those persons to whom the test may be performed.

1. Protocol Synopsis

Title:	
“Open label, Single-Center Study utilizing BIOZEK COVID-19 Antigen Rapid Test.”
 
Comparison of Biozek COVID-19 Antigen Rapid Test results performed on self-collected samples by the subjects, to results of COVID-19 RT-PCR as a standard of care.

Number of Subjects	
Planned:	Up to 250 Subjects, minimum of 30 positive and 30 negative tests.
Study Objectives:	
To assess sensitivity and specificity of BIOZEK COVID-19 Antigen Rapid Test on a self-collected sample and self-performed test by subject (nasopharyngeal swab and oral fluid).
 
To assess subject’s performance to collect samples and conduct BIOZEK COVID-19 Antigen Rapid Test.

Target Population:	Subjects, at least 18 years of age who desire a COVID-19 RT-PCR test. Subjects must meet inclusion and exclusion criteria.
Investigational Product:	
BIOZEK COVID-19 Antigen Rapid Test Cassette
 
Nasopharyngeal Swab
 
BIOZEK COVID-19 Antigen Rapid Test Cassette
 
Oral Fluid

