Comparator:	
Type of test: RT-PCR
 
Name of test: Atila BioRad
 
BioFire
 
Luminex Aires

Study Design:	Up to 250 (30 positive and 30 negative) symptomatic subjects of age 18 or older that meet the inclusion and exclusion criteria and are willing to participate will be enrolled into the BIOZEK study. All subjects will be required to sign an informed consent form. A

study personnel will collect demographics information from the subjects.

A medical staff member will measure body surface temperature prior to performing any sample collection.

Subject will have 3 tests performed in a manner described below:

1. RT-PCR test (by medical staff prior to enrollment as a standard of care procedure). Additionally, Ct and/or FAM values will be requested. The Ct (cycle threshold) is defined as the number of cycles required for the fluorescent signal to cross the threshold (i.e., exceeds background level). The lower the Ct level the greater the amount of target nucleic acid in the sample. FAM (Fluorescein) is the most commonly used fluorescent dye attachment for oligonucleotides and is compatible with most fluorescent detection equipment.

2. BIOZEK COVID-19 Antigen Rapid Test Cassette- Nasopharyngeal Swab

(via self-collection - nasopharyngeal swab sample).

Nasopharyngeal samples will be collected via self-collection and the test will be performed by the subject. The participants will follow instructions for use provided by Biozek included with the test. The subject's performance during self-collection and test performance will be monitored and recorded in a performance form. Results in 15 minutes.

3. BIOZEK COVID-19 Antigen Rapid Test Cassette- Oral Fluid (via self-collection - oral fluid sample)

Oral fluid sample will be collected via self-collection and the test will be performed by the subject. The participants will follow instructions for use provided by Biozek included with the test. The subject's performance during self-collection and test performance will be monitored and recorded in a performance form. Results in 15 minutes.

Results will be retrieved from the RT-PCR test when available and all three samples will be analyzed and compared.

Criteria for Evaluation

Safety Criteria: During self-collection, the subject will be closely monitored according to standard of care and any adverse events will be captured.

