Efficacy Criteria: Sensitivity and Specificity will be calculated separately for BIOZEK COVID-19 Antigen Rapid Test - on a self-collected, nasopharyngeal sample and for BIOZEK COVID-19 Antigen Rapid Test on the self-collected oral fluid sample.

Additionally, the result of each test performed by the subject will be compared to the RT-PCR test result.

End Points:

Sensitivity and Specificity of BIOZEK COVID-19 Antigen Rapid Test on self-collected nasopharyngeal sample.

Sensitivity and Specificity of BIOZEK COVID-19 Antigen Rapid Test on self-collected oral fluid sample.

Table of Contents

1. Protocol Synopsis	2
2. Introduction	6
3. Background	6
4. Study Objectives:	7
5. Investigational Product	7
6. Study Population	14
6.1 Inclusion Criteria	14
6.2 Exclusion Criteria	14
6.3 Sample Size	14
6.4 Confirmation of Patient Enrollment	14
6.5 Patient Identification	14
6.6 Removal, Replacement, or Early Withdrawals of Subjects	15
7. Overview of Investigational Plan and Study Administration	15
7.1 Enrollment	15
7.2 Material and Methods	15
7.3 Premature Discontinuation	16
7.4 Protocol Violations	16
7.5 Compliance	16
8. Data analysis.	17
9. Ethics	17
9.1 Hospital Ethics Committee/Institutional Review Board	17
9.2 Ethical Conduct of the Study	17
9.3 Subject Information and Consent	17
10. References	18

2. Introduction

Widespread testing is the cornerstone of COVID-19 control around the world. However, U.S. testing to identify people with infected SARS-CoV-2 has been slow to start and continues to lag. An important feature of SARS-CoV-2 is that it can be transmitted while a host is unaware of infection (asymptomatic). Epidemiologic evidence has demonstrated that pre-symptomatic and asymptomatic transmission of virus has driven the current epidemic¹. Antigen tests have a great potential for screening asymptomatic people². To limit outbreaks, testing is needed to identify as many individuals who are transmitting infection as quickly as possible. Antigen Tests have the potential to readily identify an individual who is at or near peak infection. Rapid Tests, while less sensitive, perform best during the early stages of COVID-19 infection; when viral load and potential for spread is high.

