There is an unmet need to provide broad testing that can serve high risk and low resource communities. The FDA's authorization for antigen tests for home use is helping to expand Americans' access to testing, reducing the burden on laboratories and test supplies³. The Biozek Antigen Rapid Test can be easily performed by untrained personnel with results in less than 15 minutes. The increased potential for repeated testing, remote or at home testing, could help contain the COVID-19 pandemic.

3. Background

In December 2019, an outbreak emerged identifying a novel coronavirus, severe acute respiratory syndrome coronavirus 2 (SARS-CoV-2). The World Health Organization (WHO) declared it a global pandemic in March 2020. Testing in the U.S. appeared to be insufficient for optimal early containment of the virus. With the resurgence of the disease (COVID-19), the U.S. has recently seen the highest number of hospitalizations since the beginning of the pandemic and rates are expected to increase in future weeks⁴. Given the continued community transmission of SARS-CoV-2 in the US, there has been sustained focus on the role of testing to reduce the spread. Presently, the gold standard polymerase chain reaction (PCR) test is used to diagnose COVID-19 by detecting the presence of specific genetic material of the virus. PCR test requires laboratory processing and it may take days to obtain results. In turn, an individual could be negative at time of testing but positive by the time the result is returned⁵. PCR testing is performed by a trained healthcare professional at an approved testing facility. In contrast, The BIOZEK Rapid Antigen Test detects specific proteins on the surface of the virus and it can be self-administered. Results are generated in 15 minutes and can be performed at home or any remote location. In efforts to meet the exponential demand in testing, the introduction of a new and effective Rapid Test could potentially end the spread of COVID-19.

4. Study Objectives:

To assess sensitivity and specificity of BIOZEK COVID-19 Antigen Rapid Test on a self-collected sample and self-performed test by subject (nasopharyngeal swab and oral fluid).

To assess subject's performance to collect samples and conduct BIOZEK COVID-19 Antigen Rapid Test.

5. Investigational Product

[figure not shown]

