7.2 Material and Methods

The Enrollment population consists of up to 250 (minimum of 30 positive and 30 negative samples) symptomatic patients. Enrollment will take place at the subject's home during scheduled visits to patients appointed for an RT-PCR test, as the standard of care procedure, performed by a medical staff member. Medical staff members will perform the RT-PCR test and the samples will be sent to A2Z Diagnostics Laboratory. The results will be available in 1-3 days. Results including Ct and/or FAM values of the RT-PCR test from subjects enrolled to the study will be collected by study personnel.

After completion of the RT-PCR Test, the patients will be asked if they are willing to participate in the BIOZEK Study. If the subject is age 18 or older and meets the inclusion and exclusion criteria, they will sign an Informed Consent Form and will be enrolled into the BIOZEK study. A study personnel will collect demographics information from the subjects; in addition, they will take the subject's body's surface temperature and capture it in the CRF.

Subject will perform 2 additional tests performed in a manner described below:

1. BIOZEK COVID-19 Antigen Rapid Test Cassette-Nasopharyngeal Swab (via self-collection - nasopharyngeal swab sample),

Nasopharyngeal samples will be collected via self-collection and the test will be performed by the subject. The participants will follow instructions for use provided by Biozek included with the test. The subject's performance during self-collection and test performance will be monitored and recorded in a performance form. Results in 15 minutes.

2. BIOZEK COVID-19 Antigen Rapid Test Cassette-Oral Fluid (via self-collection - oral fluid sample)

Oral fluid sample will be collected via self-collection and the test will be performed by the subject. The participants will follow instructions for use provided by Biozek included with the

test. The subject's performance during self-collection and test performance will be monitored and recorded in a performance form. Results in 15 minutes

Test Results

After interpreting the results, the coordinator will take an image of the cassette to be recorded and captured in the CRF. Compliant to all procedures required for disposal of biohazardous waste.

Results will be retrieved from the PCR test when available and all three samples will be analyzed and compared.

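### Is a minimum of 30 positive results too few, given that the plan allows 250 subjects?

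*Combined protocol and SAP*

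**What the plan says.** Section 6.3 (Sample Size) has two sentences. The first is a cap, "Up to 250 subjects will be enrolled in the study", and the second a floor, "The study shall be continued until at least 30 positive and 30 negative tests results are obtained". The same numbers recur in the synopsis under Number of Subjects ("Up to 250 Subjects, minimum of 30 positive and 30 negative tests"), in the synopsis under Study Design ("Up to 250 (30 positive and 30 negative) symptomatic subjects of age 18 or older") and in section 7.2 ("up to 250 (minimum of 30 positive and 30 negative samples").

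The endpoints are sensitivity and specificity of each Biozek cassette: "Sensitivity and Specificity will be calculated separately for BIOZEK COVID-19 Antigen Rapid Test", once for the nasopharyngeal sample and once for the oral fluid sample. Section 8 names RT-PCR as the reference and says that the two measures will be computed. The protocol gives no hypothesis, acceptance threshold, target interval width, expected sensitivity or expected RT-PCR positivity.

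**The concern.** In a study that tests no hypothesis, sample size has one job, which is to make the estimates precise. Here the size rule can be met with sensitivity resting on 30 infected people, and no passage explains the number. The Introduction concedes "Rapid Tests, while less sensitive, perform best during the early stages of COVID-19 infection" and then argues for wide use: "The increased potential for repeated testing, remote or at home testing, could help contain the COVID-19 pandemic". The share of infected people who would be missed is therefore the figure that readers most need. With 24 of 30 detected, the exact interval is compatible with missing anything from 8% to 39% of them. The plan already permits 250 subjects, so ending at 30 positives appears to give away precision that was within reach.

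Specificity has a similar limit when positivity is about 50% or more and the 30 negatives become the binding floor. Even 30 of 30 correct leaves a lower 95% limit of 88 to 89%.

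**Working it through.** **Inputs.** From the documents: cap 250, floor 30 positive and 30 negative. Assumed, because the documents give no values: two-sided 95% intervals, sensitivity 80% (90% also shown), RT-PCR positivity 10 to 50%, and 'positive' read as RT-PCR positive, the denominator of sensitivity. The protocol states no precision figure, so there is nothing to reproduce first.

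**1. Interval width at the floor.** The Wilson limits are

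[p + z²/(2n) ± z·√(p(1−p)/n + z²/(4n²))] / (1 + z²/n).

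With p = 0.80, n = 30 and z = 1.96, the centre is 0.766 and the half-width 0.139, so the limits are 62.7% and 90.5%. Other cases:

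| Detected / positives | Wilson 95% | Width | Exact width |
|---|---|---|---|
| 24/30 | 62.7–90.5 | 27.8 | 30.9 |
| 40/50 | 67.0–88.8 | 21.8 | 23.7 |
| 48/60 | 68.2–88.2 | 20.0 | 21.5 |
| 60/75 | 69.6–87.5 | 17.9 | 19.2 |
| 100/125 | 72.1–86.1 | 13.9 | 14.7 |
| 27/30 | 74.4–96.5 | 22.2 | 24.4 |
| 28/30 | 78.7–98.2 | 19.5 | 21.3 |

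The last two rows show how far the 28 points depend on the assumed 80%.

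**2. What the 250 would add.** Expected enrolment to reach 30 positives is 30/positivity: 30/0.20 = 150 and 30/0.30 = 100. At 50% positivity both floors bind, and simulation gives a mean of 66. Positives among all 250 are 250 × 0.20 = 50, 250 × 0.30 = 75 and 250 × 0.50 = 125. At 20% positivity the gain is 27.8 − 21.8 = 6.0 points (Wilson) or 30.9 − 23.7 = 7.2 (exact), for 250 − 150 = 100 more subjects. At 12% positivity, 250 × 0.12 = 30: the cap and the floor coincide and nothing is gained.

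**3. What a higher floor would add.** The binomial probability of at least 60 positives in 250 is 0.07 at 20% positivity, 0.67 at 25% and 0.985 at 30%. With a 60/60 floor, mean enrolment rises from 150 to 249 at 20% positivity, from 100 to 200 at 30% and from 66 to 129 at 50%. At 20% the cap would nearly always come first, with about 50 positives.

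**4. Chance error at 30 positives.** With true sensitivity 80%, the probability that the estimate is 70% or less, or 90% or more, is 25.1% for n = 30, 7.4% for n = 60 and 2.9% for n = 75. These figures depend on the boundary. At n = 30, the counts 21 and 27 lie exactly 10 points from the truth and carry 6.8% + 7.9% = 14.6% (rounded from unrounded terms). Counting only errors above 10 points gives 10.5%, 3.4% and 2.9%.

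**5. Which test is counted.** The four passages speak of tests, test results, subjects and samples, and none names RT-PCR. If Biozek positives were counted instead, 30 of them would imply about 30/0.80 = 37.5 RT-PCR positives, ignoring false positives. The Wilson width for 30/38 is 25.3 points. RT-PCR is the natural reading, since it defines both denominators, and it is the less favourable of the two.

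**The case for a change.** The strongest case for a change is that a floor which also ends the duty to enrol is the only precision the plan guarantees. Precision lost by an early end cannot be recovered in the analysis. More subjects would narrow the interval at any sensitivity from 70 to 95%, so the argument does not hang on the assumed 80%. The extra subjects fit within the cap and could be enrolled at visits already scheduled for the standard-of-care RT-PCR. Losses could erode the count further: section 6.6 does not replace withdrawals, and a cassette can read invalid.

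Much of this stands. A study that ends at 30 positives complies with the protocol, its interval is wide, and a sentence explaining the 30 would have helped the reader.

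It does not establish a defect. A width of 20 points, or a count of 60, would be the reviewer's target and not the plan's. Sixty positives reach 20 points only by Wilson; the exact interval needs about 70. The cap says how many subjects may be enrolled and does not promise that number. RT-PCR results also take one to three days (section 7.2), so some enrolment past the floor is likely, and the figures for an immediate end are lower-end cases.

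**Conclusion.** No change to the plan follows. Section 6.3 permits a small study, and its consequence is correctly sized: about 28 points (Wilson) or 31 (exact) at 80% sensitivity with 30 RT-PCR positives, and 22 to 24 points at 90%. That contradicts nothing in the protocol, which promises no width, power or threshold. Enrolling further would buy 6 to 7 points at 20% positivity for about 100 more subjects, more at higher positivity, and nothing at about 12% or below. This is a fair trade-off between effort and precision, and it belongs to the sponsor.

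The remaining gaps are ones that analysts fill sensibly. They would take RT-PCR as the count that defines the denominators, and would print a 95% interval beside each sensitivity and specificity. Writing into section 6.3 that a wide interval is accepted would alter no estimate and no conclusion. A reader who sees 24/30 with its interval can judge how far the result goes. The conclusion rests on the study staying descriptive; a stated performance threshold would require the size to be justified against it.

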6.4 Confirmation of Patient Enrollment

Patient enrollment into the study will be confirmed by on-site Study Monitor.

6.5 Patient Identification

During the study, the Study Monitor will submit a daily summary to Quality Research and Invention LLC, with the total number of subjects enrolled that day to the study. Patient numbers will be assigned sequentially as patients are enrolled at the site. Once assigned, patient numbers will not be re-used. Each patient's screening number will be recorded on every page of the CRF. In any correspondence or communication with the Sponsor, patients should be referred to by the screening number and initials only.

6.6 Removal, Replacement, or Early Withdrawals of Subjects

Patients who withdraw following the commencement of study treatment due to any reason will not be replaced.

7. Overview of Investigational Plan

7.1 Enrollment

- Participants will be recruited;
- Subject to be screened and deemed eligible by the study personnel for enrollment;
- Patient details to be entered onto the information form;
- Site enrolls patients and assigns patient screening numbers.

7.2 Material and Methods

The Enrollment population consists of up to 250 (minimum of 30 positive and 30 negative samples) symptomatic patients. Enrollment will take place at the subject's home during scheduled visits to patients appointed for an RT-PCR test, as the standard of care procedure, performed by a medical staff member. Medical staff members will perform the RT-PCR test and the samples will be sent to A2Z Diagnostics Laboratory. The results will be available in 1-3 days. Results including Ct and/or FAM values of the RT-PCR test from subjects enrolled to the study will be collected by study personnel.

After completion of the RT-PCR Test, the patients will be asked if they are willing to participate in the BIOZEK Study. If the subject is age 18 or older and meets the inclusion and exclusion criteria, they will sign an Informed Consent Form and will be enrolled into the BIOZEK study. A study personnel will collect demographics information from the subjects; in addition, they will take the subject's body's surface temperature and capture it in the CRF.

Subject will perform 2 additional tests performed in a manner described below:

1. BIOZEK COVID-19 Antigen Rapid Test Cassette-Nasopharyngeal Swab (via self-collection - nasopharyngeal swab sample),

Nasopharyngeal samples will be collected via self-collection and the test will be performed by the subject. The participants will follow instructions for use provided by Biozek included with the test. The subject's performance during self-collection and test performance will be monitored and recorded in a performance form. Results in 15 minutes.

2. BIOZEK COVID-19 Antigen Rapid Test Cassette-Oral Fluid (via self-collection - oral fluid sample)

Oral fluid sample will be collected via self-collection and the test will be performed by the subject. The participants will follow instructions for use provided by Biozek included with the

test. The subject's performance during self-collection and test performance will be monitored and recorded in a performance form. Results in 15 minutes

Test Results

After interpreting the results, the coordinator will take an image of the cassette to be recorded and captured in the CRF. Compliant to all procedures required for disposal of biohazardous waste.

Results will be retrieved from the PCR test when available and all three samples will be analyzed and compared.

All data collected from the three samples will be transferred to Quality Research and Invention, LLC for analysis.

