POSITIVE: * Two red lines appear. One red line should be in the control region (C) and another red line should be in the test region (T). Positive result in the test region indicates detection of COVID-19 antigens in the sample. *NOTE: Red color line intensity in the test region (T) will vary based on the amount of COVID-19 antigen present in the sample. Any shade of red color in the test region (T) should be considered positive.

[figure not shown]
NEGATIVE: One red line appears in the control region (C). No apparent red line appears in the test region (T) indicates a negative COVID-19 antigen test result.

INVALID: No red line appears in the control region (C). Insufficient specimen volume or incorrect procedural techniques are the most likely reasons for control line failure. Review the procedures and repeat the test with a new cassette. If the problem persists, discontinue using the test kit immediately and contact your local BIOZEK products distributor.

Specimen Collection - Oral Fluid

[figure not shown]
Content

Advise the patient not to consume food, beverages, chewing gum, tobacco, and other substances at least 10 minutes prior to specimen collection.

Step 1

Connect the plastic tube (number 2) to the mouthpiece (number 1). Press the plastic tube as far as possible into the mouthpiece.

Step 2

If you are having trouble collecting saliva in your mouth, try closing your mouth and wiggling your tongue. Gently rubbing the outside of your cheeks, just behind your back teeth. Making chewing motions with your mouth.

NOTE: We recommend carrying out this step in the morning.

Step 3

Spit the oral fluid into the mouthpiece. There should be about 0.5 ml of liquid in the plastic tube. This corresponds to the bottom line on the plastic tube.

[figure not shown]

Step 4a

Remove the mouthpiece (number 1) and dispose of it in the specimen bag (number 8). Place the plastic tube in the holder (number 6).

Step 4b (only follow this step if there is too much saliva)

[figure not shown]
More than 0.5 ml of liquid? Take the pipette (number 3). Press and hold the bulb until the pipette protrudes into the solution of the plastic tube (1). Release the balloon slowly, so that the pipette sucks up the solution (2). Bring the liquid level to the bottom line (0.5 ml).

Specimen Extraction – Oral Fluid

Step 5

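### The plan sets no order for the two self-read Biozek cassettes beyond listing the swab first, and nothing keeps one result from influencing the reading of the other.

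*Combined protocol and SAP*

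**What the plan says.** The title describes the study as "Open label, Single-Center Study utilizing BIOZEK COVID-19 Antigen Rapid Test", and no section masks any reader.

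The visit is described twice. The synopsis (Study Design) says "Subject will have 3 tests performed in a manner described below" and numbers RT-PCR, swab cassette and oral-fluid cassette in that order. Section 7.2 says "Subject will perform 2 additional tests performed in a manner described below" and numbers the swab first and oral fluid second. In both places the subject collects the sample and performs the test, and performance is observed and recorded on a form. Section 7.2 adds that the coordinator photographs the cassette for the CRF once it has been interpreted. It does not name the interpreter.

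Section 5 makes both readings visual, at 15 minutes. For the swab, "Any shade of red color in the test region (T) should be considered positive". The oral-fluid steps address the tested person as the reader.

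The synopsis (Efficacy Criteria) states that "Sensitivity and Specificity will be calculated separately for BIOZEK COVID-19 Antigen Rapid Test", once for the swab and once for oral fluid. Each cassette therefore has its own accuracy endpoint. Section 8 says only that sensitivity and specificity will be calculated against RT-PCR.

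**The concern.** Two visual readings are made by one person at one visit, and whoever reads the second cassette may already know what the first one showed. A doubtful line can then be resolved to agree with the other cassette. The accuracy obtained would be that of a cassette read with help from another test, not that of the cassette used alone at home.

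Order also matters apart from the reading. Practice on the first cassette may help with the second, or the differing steps may confuse (section 5 calls for 3 drops with the swab test and 2 with oral fluid). Subject performance is a stated objective. If sites simply follow the list, any such effect falls on oral fluid and cannot be separated from the cassette itself. Unlike sampling error, a bias of this kind does not shrink as enrolment moves from the minimum towards 250, and no interval reflects it.

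**Working it through.** **1. What the text fixes and what it leaves open.**

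| Question | Synopsis and 7.2 | Section 5 | Section 8 |
|---|---|---|---|
| Order of the two cassettes | Swab listed first; no rule on sequence, no alternative | Silent | Silent |
| Reader | Subject performs the test; interpreter not named | Oral-fluid steps address the tested person | Silent |
| One reading kept from the other | No | No | No |
| Order and read times recorded | Not stated | Not stated | Not stated |
| Later masked reading of the images | None planned | None | None |

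The plan gives no figure for this effect, so there is none to reproduce. The minimum of 30 positive and 30 negative results comes without a precision target or assumed accuracy, and the point does not depend on it.

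**2. Borderline-line model (all inputs assumed).** Let b be the share of RT-PCR positives with a borderline oral-fluid line, s the probability that the swab is positive in those subjects, and h the probability that the line would be called positive without sight of the swab. If borderline lines follow the swab, the shift in oral-fluid sensitivity is b × (s − h).

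- s = 0.80, h = 0.50: b = 0.05, 0.10, 0.20 gives b × 0.30 = +1.5, +3.0, +6.0 points.
- s = 0.80, h = 1.00 (every faint line called positive): b = 0.05 to 0.20 gives b × (−0.20) = −1 to −4 points.
- s = 0.50, h = 0.50: 0.
- s = 0.40, h = 0.50: b × (−0.10) = −0.5 to −2 points.

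In RT-PCR negatives, with 2 to 5% borderline lines, swab specificity 98% and h = 0.50, the false-positive rate shifts by b × (0.02 − 0.50) = −1.0 to −2.4 points.

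**3. Discordance model (all inputs assumed).** Let each oral-fluid reading that disagrees with the swab be switched with probability q. Then observed oral-fluid sensitivity = So + q × (Sn − So), where Sn and So are the true swab and oral-fluid sensitivities.

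| Sn | So | q = 0.10 | q = 0.25 | q = 0.50 |
|---|---|---|---|---|
| 0.80 | 0.60 | +2 | +5 | +10 |
| 0.80 | 0.80 | 0 | 0 | 0 |
| 0.70 | 0.80 | −1 | −2.5 | −5 |

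The same formula for specificity gives +0.4 to +2 points if the swab is the more specific test (0.99 against 0.95), and −0.4 to −2 if it is the less specific (0.95 against 0.99).

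**4. What alternating the order does.** Take Sn = 0.80, So = 0.60, q = 0.25; the true gap is 0.20.

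- Swab always first: oral fluid 0.60 + 0.25 × 0.20 = 0.65, swab 0.80, gap 0.15.
- Alternated, so half of each is exposed: oral fluid 0.60 + 0.125 × 0.20 = 0.625, swab 0.80 − 0.125 × 0.20 = 0.775, gap 0.15.
- Only the readings made first, if they are recorded before the other result is seen: 0.60 and 0.80, gap 0.20.

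Alternation alone spreads the bias. Alternation with the first reading locked in leaves about half of each cassette's readings free of it.

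**5. Precision of a split by order.** Taking the minimum of 30 as RT-PCR positives, 30 / 2 = 15 per order. An observed 12/15 has an exact 95% interval of 0.52 to 0.96. The difference between orders at 80% has a half-width of about 1.96 × √(2 × 0.80 × 0.20 / 15) = 0.29, or 29 points.

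**The case against.** The strongest reply is that the numbered lists describe how each test is done, not when. Where the protocol fixes timing it says so, as in placing RT-PCR before enrolment. This stands. A reader might infer that every subject does the swab first and that oral fluid carries all the carry-over, but the documents do not say that. Side-by-side running is equally permitted, and it would expose both readings.

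A reader might also infer that the oral-fluid results will be flattered. The working does not support that: the sign for sensitivity reverses with plausible changes to assumed inputs. Nor can the any-shade rule be carried over to oral fluid. It appears only in the swab instructions, where it narrows discretion, and some figures in the oral-fluid instructions are not shown, so their reading guidance cannot be judged.

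It would also be too strong to say that the data could never reveal the problem. Cassette images go into the CRF, and a masked re-read could show a pull towards the other result. None is planned, however.

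Three further points are fair. RT-PCR results come 1 to 3 days later, so readings are normally made without the reference result; that gives no protection against seeing the other cassette. There is no formal swab-versus-oral endpoint, only a general statement that the three samples will be compared, so the main stake is each cassette's own accuracy. And reading by the subject is the intended use of a self-test, so it is not at fault here. If the coordinator were the interpreter, that reader would be equally unmasked.

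**Conclusion.** The point holds as a gap in design. Following the plan as written lets one cassette's result influence the reading of the other, for endpoints that are meant to stand separately. This rests on the text alone: both visit descriptions list one order and provide for no other, the same unmasked person handles both cassettes, and no step separates the readings.

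Which endpoint is affected depends on how visits are run, and the plan does not settle that. The size of the bias, and its direction for sensitivity, cannot be derived from the documents. Under the assumed inputs most shifts are a few points either way, reaching +10 only if half of all discordant readings are switched and the swab is 20 points more sensitive. This is smaller than the sampling error at 30 positives, but it is systematic and cheap to prevent. Order and independent first readings cannot be recovered once visits are over.

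**What to change.** In section 7.2 and the synopsis:

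- Assign the order of the two Biozek tests by sequential patient number (odd: swab first; even: oral fluid first).
- Require the first result to be read, written on the form, and the cassette photographed and removed from view, before the second cassette is read.
- Record the order, and the start and read time of each cassette, on the performance form.

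In section 8:

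- Report each cassette's sensitivity and specificity overall and, as a descriptive sensitivity analysis, in the subjects in whom it was read first.
- State that with about 15 positives per order this analysis cannot exclude a carry-over of a few points.

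The locked-in first reading is the essential part, since alternation without it would only share the bias between the cassettes. The cost is one paragraph in each place, a few form fields and two visit flows for staff to follow. No extra subjects or samples are needed.
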